10.5 Schedule of Events

Table 8. SCREENING AND CYCLE 1

Visit/Cycle	Screening	Day -7 (Run-in Phase)	Cycle 1			
			1	2	8	15
Study Windows	-30 days	-3 days for screening tests to count for Day -7			±1 day	±1 day
Entospletinib		Days -7 to -1	Days 1-28			
Obinutuzumab			X	X	X	X
Informed consent	X					

Medical history	X	X	X	X	X	X
Concomitant medication (s)	X	X	X	X	X	X
Adverse events assessment		X	X	X	X	X
Height, weight	X	X				
Vital signs	X	X	X	X	X	X
ECOG performance status	X	X				
Physical examination	X	X				
12-lead ECG	X					
ECHO	X ^A					
Bone marrow aspirate and biopsy (includes biomarker aspirate)	X ^B					
Hematology	X	X	X	X	X	X
Chemistry	X	X	X ^C	X ^C	X	X
Hepatitis serologies	X					
aPTT, INR	X					
Serum immunoglobulins	X					
Reticulocyte count	X					
Direct antiglobulin test	X					
β 2-microglobulin	X					
Genetic and molecular prognostic markers	X ^D	X ^D				
Biomarker blood samples		X	X			
Serum/Urine pregnancy test	X					
Urinalysis	X					
CT neck, chest, abdomen and pelvis (with contrast when clinically acceptable) ^E	X					

KEY

^AECHO will be performed only if clinically indicated

^BBone marrow aspirate and biopsy is optional unless ANC<1,000/mm³ or platelets<50,000/mm³. Results acceptable if performed within 6 months prior to screening visit. Biomarker sample (10 mL aspirate) should be obtained (see 9.0 Correlative studies).

^COptional serum biochemistry/metabolic panel measurements may be considered by the investigator at the end of C1D1 and C1D2.

^DCLL FISH panel results acceptable if performed within 6 months prior to the first dose of study treatment, and if no intervening treatment occurred; ZAP-70 expression results acceptable if performed at any time since diagnosis and will be documented, but not required; IGHV mutational status - results acceptable if performed at any time since diagnosis. If this result is not available, testing for IGHV mutational status will be performed in [name] laboratory.

^EIn subjects with NHL (FL, MZL, MCL) – PET-CT scans *may* be performed in place of CT scans at screening, during the study and at follow-up. However, the same modality should be used for each individual patient during the study.

Table 9. CYCLE 2-

Visit/Cycle	Cycle 2-6	Cycles 7-12	Cycles 13, 14, 16, 18, 20 and then every two cycles until end of therapy
Cycle Day	1	1	1
Study Windows	+/- 3 days	+/- 3 days	+/- 7 days
Entospletinib^E	Days 1-28	Days 1-28	Days 1-28
Obinutuzumab	X		
Medical history	X	X	X
Concomitant medication (s)	X	X	X
Adverse events assessment	X	X	X
, Weight	X	X	X
Vital signs	X	X	X
ECOG performance status	X	X	X
Physical examination	X	X	X
Hematology	X	X	X
Chemistry	X	X	
CT neck, chest, abdomen and pelvis (with contrast when clinically acceptable)^A	X^B (C4D1 or \leq72 h prior)	X^B (C7D1 and C10D1 or \leq72 h prior)	C18D1 and C24D1
Assessment of B-cell depletion		X (C7D1)	
Biomarker blood sample		X (C7D1)	
Bone marrow aspirate and biopsy (includes biomarker aspirate)^C		X	X
Overall response assessment^D	X	X	X^B

KEY:

^AIn subjects with NHL (FL, MZL, MCL) – PET-CT scans *may* be performed in place of CT scans at screening, during the study and at follow-up. However, the same modality should be used for each individual patient during the study.

^BIn subjects with LPL, CT scans on C4D1, C10D1 and during follow-up will be performed only if lymphadenopathy is present at screening, or if new lymphadenopathy develops during scheduled CT scans on C7D1 or the EOT visit.

^CIf radiographic and laboratory findings suggest that CR has been obtained, a bone marrow aspirate/biopsy should be obtained to confirm CR between 1 and 3 months after the corresponding CT, accompanied by a biomarker sample (10 mL aspirate) – see 9.0, Correlative studies

^DOverall response assessment should be performed when CTs or PET-CTs are performed

^ESubjects may continue entospletinib monotherapy beyond C12.

Table 10. End of Treatment and Follow-up prior to study closure

Visit/Cycle	EOT ^F	Follow up ^F	
Cycle Day	8 weeks after last dose of study drug	Every 3 months for the first year following EOT	Every 6 months for EFS thereafter
Study Windows	+/- 7 days	+/- 7 days	+/- 2 months
Medical history	X		
Concomitant medication (s)	X		
Adverse events assessment	X		
Height, weight	X		
Vital signs	X	X	
ECOG performance status	X	X	
Physical examination	X	X	X
MRD assessment, peripheral blood	X		
Bone marrow aspirate and biopsy; includes biomarker aspirate (all patients)	X^A		
Hematology	X	X	X
Chemistry	X	X	
Serum immunoglobulins	X		
CT neck, chest, abdomen and pelvis (with contrast when clinically acceptable)^B	X	X^{C,D}	
Overall response assessment^E	X	X	
Event-free survival assessment		X	X

KEY:

^AAn optional bone marrow aspirate/biopsy should be obtained between 1 and 3 months after End of Treatment visit, accompanied by MRD assessment and a biomarker aspirate. Exception: patients who underwent a bone marrow biopsy to obtain CR confirmation after 6 cycles of therapy will not undergo EOT bone marrow biopsy

^BIn subjects with NHL (FL, MZL, MCL) – PET-CT scans *may* be performed in place of CT scans at screening, during the study and at follow-up. However, the same modality should be used for each individual patient during the study.

^CCT scans will be obtained at 6 and 12 months after the end of treatment visit (± 7 days), and as clinically indicated thereafter.

^DIn subjects with LPL, CT scans on C4D1, C10D1 and during follow-up will be performed only if lymphadenopathy is present at screening, or if new lymphadenopathy develops during scheduled CT scans on C7D1 or the EOT visit.

^EOverall response assessment should be performed when CTs or PET-CTs are performed.

^FParticipants still participating at study closure will complete an abbreviated EOT visit and no additional follow up will occur.

Table 11. Modified End of Treatment SoE: participants on study at time of study closure

Visit	EOT
Timing	At the time of study drug discontinuation
Window	+30 days
Medical History	X
Concomitant medications	X
Adverse Events Assessment	X
Height, weight	X
Vital signs	X
ECOG performance status	X
Physical examination	X
Hematology	X
Chemistry	X

11.0 MEASUREMENT OF EFFECT

All subjects who received at least one dose of study drug (ITT, section 13.3) will be evaluable for efficacy.

11.1 Disease Evaluations

Physical examination, which will focus on documenting a change in the number of sites and size of lymphadenopathy, hepatomegaly and splenomegaly, will be done as part of the full disease evaluation during treatment. More extensive physical exams will be performed if guided by the development of new symptoms.

Complete blood count (CBC) with measurement of parameters including ALC will be obtained before start of treatment (Day -7), Days 1, 2, 8 and 15 of C1; on day 1 for the remaining twelve cycles, every 3 months for the first 12 months, and every 4-6 months thereafter until disease progression or death.

Serum biochemistry/metabolic panel will be obtained on will be obtained on Days -7, 1, 2, 8 and 15 of C1; on day 1 for the remaining twelve cycles, every 3 months for the first 12 months, and every 4-6 months thereafter until disease progression or death.

Computed tomography (CT) scan of neck, chest, abdomen and pelvis with intravenous contrast where possible will be performed at screening, on C4D1, C7D1, C10D1 (or ≤ 72 hours prior), at C18D1 and C24D1 should patients opt to continue Entospletinib monotherapy

A unilateral bone marrow aspirate and biopsy must be obtained during screening or up to 6 months before the first dose of study drug. Subjects who have bone marrow aspirate and biopsy results since completion of their last therapy for CLL may use those results if they were obtained within 6 months prior to the first dose of study drug. If the subject's physical examination findings, laboratory and radiographic evaluations suggest that CR has been obtained during C7D1, a bone marrow aspirate/biopsy should be obtained to confirm the CR within the timeframe specified above.

11.2 Criteria for Response

11.2.1. Subjects with CLL/SLL

Modified IWCLL guidelines [41] will be used to measure response in CLL/SLL subjects.

ORR for CLL/SLL subjects is defined as CR, CRi, nPR and PR, PD and SD. Subjects will be assessed for response at the end of treatment. If there is a clinical suspicion for progression, disease assessment may be performed at any time.

Complete Remission (CR)

Requires all of the following:

- Peripheral blood lymphocytes (evaluated by blood and differential count) below $4 \times 10^9/L$
- Absence of significant lymphadenopathy (eg, lymph nodes >1.5 cm in diameter) by physical examination and imaging, if baseline scans were abnormal
- No hepatomegaly or splenomegaly by physical examination and imaging, if baseline scans were normal
- Absence of constitutional symptoms (B symptoms)
- Blood counts must have the following findings:
 - a) Neutrophils $> 1.5 \times 10^9/L$ without need for exogenous growth factors
 - b) Platelets $> 100 \times 10^9/L$ without need for exogenous growth factors
 - c) Hemoglobin > 11.0 g/dL without red blood cell transfusion or need for exogenous erythropoietin
- Bone marrow aspirate and biopsy must have the following findings:
 - a) Normocellular for age
 - b) Less than 30% of nucleated cells being lymphocytes
 - c) No B-lymphoid nodules (confirmed by IHC)

Complete Response with Incomplete Marrow Recovery (CRi)

Subjects who fulfill all the criteria for a CR but who have a hypocellular marrow and persistent anemia or thrombocytopenia or neutropenia unrelated to CLL but secondary to drug toxicity. If the marrow is hypocellular, a repeat determination should be performed after 4 weeks, or when peripheral blood counts have recovered.

Nodular Partial Response (nPR)

Subjects who fulfill all the criteria for CR but who have bone marrow evidence of B-lymphoid nodules by IHC.

Partial Remission (PR)

Blood count should show at least one of the following results:

- Neutrophils more than $1.5 \times 10^9/L$ without need for exogenous growth factors
- Platelet counts $> 100 \times 10^9/L$ or 50% improvement over baseline without need for exogenous growth factors
- Hemoglobin > 11.0 g/dL or 50% improvement over baseline without requiring red blood cell transfusions or exogenous erythropoietin

AND two of the following three criteria should be met:

- Decrease in number of blood lymphocytes by 50% or more from the value before therapy
- Reduction in lymphadenopathy by physical examination or by imaging as defined by:
 - A decrease in lymph node size by 50% or more either in the sum products of up to 6 lymph nodes, or in the largest diameter of the enlarged lymph node(s) detected prior to therapy
 - No increase in any lymph node, and no new enlarged lymph node
 - In small lymph nodes (< 2 cm), an increase of less than 25% is not considered significant
- A reduction in splenomegaly and hepatomegaly by 50% or more, by physical examination or imaging.

PR with Lymphocytosis

Because of the expected egress of CLL cells into the peripheral blood with BCRi, lymphocytosis may be encountered with entospletinib. Therefore progressive lymphocytosis without other clinical evidence of disease progression cannot be used to define disease progression. Accordingly, lymphocyte count will be ignored in the evaluations of progression. Of note, this has been an accepted standard in trials using inhibitors of B-cell receptor signaling for the treatment of CLL.

Furthermore, lymphocytosis should not interfere at the time of designation of a PR. PR with lymphocytosis should be based on other measurable aspects of disease other than ALC [45].

Progressive Disease

Includes at least one of the following:

- Appearance of any new lesion, such as enlarged lymph nodes > 1.5 cm, splenomegaly, hepatosplenomegaly, or other organ infiltrates.
- An increase by 50% or more in greatest determined diameter of any previous site including, liver and/or spleen,
- A 50% or greater increase in lymphocyte count.
- Transformation to a more aggressive histology (eg, Richter syndrome). Whenever possible this diagnosis should be established by lymph node biopsy.

Progressive Disease After Treatment

Includes at least one of the following:

- Any progressive disease criteria listed above
- The progression of any cytopenia (unrelated to autoimmune cytopenia) which occurs at least 3 months after treatment as documented by:
 - a decrease in Hb levels by more than 20 g/L (2 g/dL) or to less than 100 g/L (10 g/dL), OR
 - a decrease of platelet counts by more than 500,
- OR
- a decrease of platelet counts by more than 50% or to less than $100 \times 10^9/L$ ($100\,000/\mu L$).

Stable Disease

Patient who have not achieved a CR or a PR, and who have not exhibited progressive disease, will be considered to have stable disease (which is equivalent to a nonresponse).

11.2.2. Subjects with Follicular Lymphoma, Marginal Zone Lymphoma and Mantle Cell Lymphoma (enrolled on Phase I portion of the study) – See Appendix G

The determination of MZL and MCL response and progression will be based on standardized response criteria for malignant lymphoma [46].

11.2.3. Subjects with Lymphoplasmacytic Lymphoma (enrolled on Phase I portion of the study) – See Appendix E

11.2.4. Subjects with Hairy cell Leukemia (enrolled on Phase I portion of the study) – See Appendix I

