10.2.1 Pre-Treatment Criteria - Day -7

Hematologic parameters: platelets must be $\geq 50,000/\text{mm}^3$ (in absence of transfusion support), ANC $\geq 1000/\text{mm}^3$ unless due to disease involvement in the bone marrow; hemoglobin $> 8 \text{ g/dL}$ (transfusion support permissible);

Non-hematologic parameters: bilirubin (total, and if elevated – direct) $\leq 2 \times$ institutional ULN (unless due to known Gilbert's syndrome or hemolysis directly attributable to CLL/SLL); AST or ALT $< 2.5 \times$ institutional ULN.

Vital signs, all laboratory data (including pregnancy testing) must be reviewed by the treating physician prior to administering the first dose of a study agent.

The study treatment period ends on day 28 of the last cycle of study treatment. Subjects will return to the study site 2 months (± 7 days) after the last 28-day cycle of study treatment for an End of Treatment visit unless early study closure procedures are in affect (see section 5.4). A bone marrow biopsy will be performed no later than 3 months after the End of Treatment visit unless early study closure procedures are in affect (See section 5.4). Adverse events that are related to study treatment and are ongoing at the time of this visit will be followed until resolution or until considered irreversible by the sponsor-investigator unless early study closure procedures are in affect.

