The phase II study will begin after determination of MTD. The Phase 2 study of the effect of treatment is designed as a single-stage study with a primary endpoint of efficacy (response rate: ORR, CR). [The study will go back to the Phase I stage if 2 or more out of the first six subjects \(including those treated in the Phase I\) receiving the currently identified MTD experience DLT](#)

13.2 Primary and Secondary Endpoints:

13.2.1 Primary Endpoints:

The primary endpoint of the Phase I portion of the study is to determine the maximum tolerated dose (MTD) and/or a recommended Phase II dose (RP2D) of entospletinib in combination with obinutuzumab in patients with relapsed/refractory chronic lymphocytic leukemia/small lymphocytic lymphoma (CLL/SLL) and NHL (FL, MCL, LPL, MZL) as measured by the incidence of dose limiting toxicities (see Section 5.2).

The primary efficacy endpoint of the Phase 2 portion of the study is the CR, defined as the proportion of subjects who achieve CR described in the section 11.2.1

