13.4.1 Analysis of Primary Endpoints

The MTD will be determined according to 3+3 dose escalation design using the dose determining set. Adverse events will be graded and categorized according to the CTCAE v4.03. All adverse events will be tabulated and summarized by major organ category, grade, anticipation, and drug attribution. SAE specific incidence and exact 95% confidence interval will be provided where appropriate.

The CR will be computed and presented together with the exact 95% confidence interval (CI), using the method of Clopper and Pearson. A null hypothesis of a 20% CR will be rejected if at least 7 of 17 patients achieve a CR and a treatment arm will not be considered further if this threshold is not reached.

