13.5 Sample Size and Power

Determination of phase I sample size

3+3 dose escalation scheme will be utilized, with 3 to 6 evaluated at each dose level. It is expected that maximum of 12 patients will be enrolled.

Determination of phase II sample size

Entospletinib has been associated with an ORR 61% at the end of study and obinutuzumab in combination with chlorambucil has led to an ORR of 77.3% and CR rate of 20.7% after completion of therapy [22]. The null hypothesis that the true CR rate is 20% will be tested against a one-sided alternative. A sample size of 17 achieves 83% power to detect a difference in complete response of 0.30 (0.2 vs. 0.5) using a one-sided binomial test with the target significance level of 0.05. The actual significance level achieved by this test is 0.0984. If more than equal to 7 patients achieve complete response, then conclude the regimen is effective, and consider a larger/next phase of clinical trial (phase III).

A sample size of 17 subjects treated at the RP2D provides a reasonable probability to detect a rare adverse event, for example, 83% chance of detecting an adverse event with an incidence of 10% (Table 14). Subjects with CLL treated at the RP2D in Phase I will be counted towards Phase II enrollment. Anticipating an attrition rate of 15%, a total of 20 patients per protocol population will need to be enrolled.

Table 14. Probability of detecting an AE with a specified incidence rate at the RP2D

AE incidence	N=17: Probability of detect an AE
0.01	0.16
0.05	0.58
0.10	0.83
0.15	0.94
0.20	0.98

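### The complete remission rule behind the Phase 2 primary endpoint waives the liver and spleen requirement for patients whose baseline scans were abnormal

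*Combined protocol and SAP*

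**What the plan says.** Section 11.2.1 sets out CR for CLL/SLL as a list in which every item must be met. The node item requires absence of significant lymphadenopathy "by physical examination and imaging, if baseline scans were abnormal". The next item, the only one on the liver and spleen, reads "No hepatomegaly or splenomegaly by physical examination and imaging, if baseline scans were normal". CRi and nPR are defined by reference to the same CR criteria.

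Section 13.2.1 makes this text the Phase 2 primary endpoint, "defined as the proportion of subjects who achieve CR described in the section 11.2.1". Section 13.4.1 gives the decision rule: "A null hypothesis of a 20% CR will be rejected if at least 7 of 17 patients achieve a CR". Section 13.5 plans 17 patients for 83% power at a 50% CR rate, with a one-sided target level of 0.05.

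Section 11.2.1 also says that modified IWCLL guidelines will be used, but does not identify what was modified.

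**The concern.** The two neighbouring items carry opposite baseline conditions. For nodes, disease on the baseline scan triggers the requirement. For the liver and spleen, it removes the requirement for the very patients who have enlargement to resolve. Such patients can enrol, because splenomegaly features in one of the six alternative treatment criteria in section 3.1.

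The trial has no control arm in which a lenient definition would cancel out. The observed CR count is set against a fixed 20%, so the definition bears directly on whether the regimen is declared effective. Two assessors could also classify the same patient differently, depending on whether they follow the printed item or its apparent intent.

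**Working it through.** **1. What the item does as written.** The condition can be read in two ways.

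- (a) It governs both examination and imaging. A patient with organ enlargement on baseline scans then has no liver or spleen requirement at all.
- (b) It governs imaging only. A palpable organ still bars CR, and only enlargement visible on imaging alone escapes.

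Under either reading, some persistent baseline enlargement is compatible with CR.

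**2. Comparison with the protocol's other rules.**

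| Rule | Organ enlarged at baseline |
|---|---|
| CLL/SLL CR, section 11.2.1 | No requirement under (a); imaging requirement waived under (b) |
| CLL/SLL PR, section 11.2.1 | Reduction of at least 50% is one of three criteria, two of which are needed |
| LPL CR, Appendix E | Spleen must resolve |
| FL, MZL and MCL CR, Appendix G | Spleen and liver must return to normal |
| HCL CR, Appendix I | Any organomegaly must normalise |

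The appendices cover other histologies and serve only as comparators, but all three ask for resolution.

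**3. Does the confirmatory marrow close the gap?** Only in part. Section 11.1 triggers it when "physical examination findings, laboratory and radiographic evaluations suggest that CR has been obtained during C7D1", and persistent enlargement would ordinarily argue against that. However, suspicion of CR is judged against the same faulty criteria. Key C of Table 9 omits examination: "radiographic and laboratory findings suggest that CR has been obtained, a bone marrow aspirate/biopsy should be obtained to confirm CR". Section 10.2.1 also has a biopsy that does not depend on suspected CR: "A bone marrow biopsy will be performed no later than 3 months after the End of Treatment visit". On that last point the documents conflict, since section 10.4 and key A of Table 10 call the end-of-treatment marrow optional. In any case a marrow result says nothing about organ size.

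**4. The decision rule.** Inputs from sections 13.4.1 and 13.5: n = 17, success at 7 or more CRs, null 0.20, alternative 0.50. With X ~ Binomial(17, p):

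- Power: P(X ≥ 7 | p = 0.50) = 0.8338, which reproduces the stated 83%.
- Type I error: P(X ≥ 7 | p = 0.20) = 0.0377, which meets the 0.05 target.
- Section 13.5 instead states: "The actual significance level achieved by this test is 0.0984". That figure does not match the 7-of-17 rule. A cut-off of 6 would give 0.1057. This is a separate discrepancy and carries no weight here.

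**5. Sensitivity to over-calling (illustration only).** Let e be the share of patients with baseline organ enlargement. Let q be the chance that such a patient keeps the enlargement, meets every other CR criterion and is called CR. With a true CR rate of 20%, the apparent rate is p = 0.20 + e × q. The documents give neither e nor q; the ranges below are assumptions.

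| e | q | Over-call (points) | P(X ≥ 7) |
|---|---|---|---|
| – | – | 0 | 0.038 |
| 20% | 2% | 0.4 | 0.042 |
| 40% | 2% | 0.8 | 0.046 |
| 20% | 5% | 1.0 | 0.048 |
| 60% | 2% | 1.2 | 0.050 |
| 20% | 10% | 2.0 | 0.060 |
| 40% | 5% | 2.0 | 0.060 |
| 60% | 5% | 3.0 | 0.074 |
| 40% | 10% | 4.0 | 0.089 |
| 60% | 10% | 6.0 | 0.127 |

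Solving P(X ≥ 7) = 0.05 gives p = 0.2119, an over-call of 1.2 points. Solving for 0.0984 gives p = 0.2452, or 4.5 points.

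**6. Fragility at the boundary.** P(X = 6 | p = 0.20) = 0.068. If the true count is 6, one over-called patient reverses the conclusion.

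**The case against.** The strongest reply is that this is a one-word slip with the intent in plain view. The category is complete remission, PR already credits shrinkage of the liver and spleen, and the section names modified IWCLL guidelines as the standard. Section 10.4 also names a separate published standard for reading CT scans. Sensible assessors would apply the intended rule, and no over-call has been shown.

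Part of this stands. The slip may do no harm in practice, and the figures in step 5 are assumption throughout: three of the nine combinations stay below 0.05, a fourth sits at it, and only the most extreme exceeds 0.0984. The exact level of 0.0377 leaves some slack, and the boundary argument applies to any single misclassification. But the modifications to the guideline are not listed, the protocol does not spell out an organ rule for CLL under the CT-reading standard, and section 13.2.1 points to section 11.2.1 as the endpoint definition. Nothing in the documents overrides the printed item.

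A second reply is that changing the condition to abnormal would match the node item and Appendices E and G, and that an unconditional rule could deny CR for enlargement from other causes; Appendix G warns that an enlarged spleen may not reflect lymphoma. That is a real cost. However, the current text already bars organ enlargement in patients with normal baseline scans. A swap would drop that bar, and the progressive disease criterion for new lesions names splenomegaly and hepatosplenomegaly but not isolated hepatomegaly. Its list is illustrative, so the gap is not certain, but deletion avoids relying on it.

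**Conclusion.** The concern holds. The CR definition for the primary endpoint is wrong as written and must be corrected. Confidence in that is high, because it rests on the text alone: one liver and spleen item, conditioned the wrong way round, in the definition on which the 7-of-17 decision depends.

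The direction is clear: relative to a criterion applied to every patient, the wording can only add CRs. The size is not identifiable from the documents. Under the assumed ranges, the false-positive probability moves from 0.038 to between 0.042 and 0.127. Reading (b) lets fewer patients escape than reading (a), so its effect should be smaller. The judgement does not depend on any of these values or on an over-call having occurred.

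**What to change.** In the CR list of section 11.2.1, delete the baseline-scan clause from the liver and spleen item, so that absence of hepatomegaly and splenomegaly on examination and imaging is required of every patient. Do not simply swap the one word. If responses have already been assessed, recheck CR calls (and CRi and nPR, which inherit the criteria) in patients with organ enlargement at baseline.

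The cost is one clause in an amendment. CT is already scheduled in section 11.1, and section 10.4 already requires examinations to document liver and spleen changes, so a recheck uses data in hand. N = 17, the threshold of 7 and the power of 0.834 are unaffected.

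A minor, separate correction can go into the same amendment. The ORR sentence in section 11.2.1 includes PD and SD, contrary to section 1.2 and to the statement in section 11.2.1 that stable disease is a nonresponse. Limit it to CR, CRi, nPR and PR.

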1.2 Secondary objectives

Secondary endpoints of phase 2 portion of study are the following:

- Objective response rate (ORR, defined as complete remission, complete response with incomplete marrow recovery, partial remission and nodular partial response)
- Event free survival defined as the interval between the date of first study treatment and the date of objective signs of disease recurrence, subsequent anti-leukemic therapy, or death, whichever is first reported
- Safety and tolerability of entospletinib in combination with obinutuzumab by AEs

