3.0 STUDY POPULATION

3.1 Inclusion Criteria

3.1.1 Patients who are \geq 18 years of age, who have the following diagnosis:

Phase I portion of the study:

- histologically or flow cytometry confirmed diagnosis of B-CLL/SLL according to NCI-WG 1996 guidelines [40].
- the following types of NHL as documented by medical records and with histology based on criteria established by the WHO:
 - Mantle cell lymphoma (MCL),
 - Follicular lymphoma (FL) - grades 1-3a,
 - Lymphoplasmacytic lymphoma (LPL),
 - Marginal zone lymphoma (MZL),
 - CLL in Richter's transformation,
 - B-cell prolymphocytic leukemia
- patients with histologically confirmed classical Hairy cell leukemia (HCL)

Phase II portion of the study

- histologically or flow cytometry confirmed diagnosis of B-CLL/SLL according to NCI-WG 1996 guidelines. Patients who lack CD23 expression on their leukemia cells should be examined for (and found NOT to have) either t(11;14) or cyclin D1 overexpression, to rule out mantle cell lymphoma.

3.1.2. Patients underwent \geq 1 prior chemotherapy-based or immunotherapy-based regimen or targeted therapy (e.g., inhibitors of BTK, PI3K etc.) administered for \geq 2 cycles, , and have had either documented disease progression or no response (stable disease) to the most recent treatment regimen.

Additional disease-specific criteria:

Patients with CLL/SLL must demonstrate active disease meeting at least 1 of the IWCLL 2008 criteria for requiring treatment [41]:

- i) A minimum of any one of the following constitutional symptoms:
 - Unintentional weight loss >10% within the previous 6 months prior to screening.
 - Extreme fatigue (unable to work or perform usual activities).
 - Fevers of greater than 100.5 F for ≥ 2 weeks without evidence of infection.
 - Night sweats without evidence of infection.
- ii) Evidence of progressive marrow failure as manifested by the development of, or worsening of anemia or thrombocytopenia.
- iii) Massive (i.e., >6 cm below the left costal margin), progressive or symptomatic splenomegaly.
- iv) Massive nodes or clusters (i.e., >10 cm in longest diameter) or progressive lymphadenopathy.
- v) Progressive lymphocytosis with an increase of $>50\%$ over a 2-month period, or an anticipated doubling time of less than 6 months.
- vi) Autoimmune anemia or thrombocytopenia that is poorly responsive to corticosteroids.

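### Section 11.2.1 counts SD and PD inside ORR, and its PR rule does not say how to score disease compartments that were normal at baseline

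*Combined protocol and SAP*

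**What the plan says.** **ORR.** Section 1.2 names ORR as a secondary objective of phase 2 and defines it as "complete remission, complete response with incomplete marrow recovery, partial remission and nodular partial response". Section 11.2.1, which sets the response criteria, says instead that "ORR for CLL/SLL subjects is defined as CR, CRi, nPR and PR, PD and SD". Further down, 11.2.1 describes stable disease as equivalent to a nonresponse. Section 13.2.2 lists ORR without defining it, and 13.4.2 says only that it will be summarized with 95% confidence intervals.

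**PR.** Section 11.2.1 asks for at least one of three blood-count results (neutrophils, platelets, hemoglobin), "AND two of the following three criteria should be met":

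- lymphocytes: "Decrease in number of blood lymphocytes by 50% or more from the value before therapy"
- nodes: a reduction in lymphadenopathy by half, in the sum of products or "in the largest diameter of the enlarged lymph node(s) detected prior to therapy"
- organs: "A reduction in splenomegaly and hepatomegaly by 50% or more, by physical examination or imaging"

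None of the three is conditioned on the compartment being abnormal at baseline. The CR node criterion in the same section does carry such a condition. A later paragraph says that lymphocytosis should not interfere with calling a PR and that "PR with lymphocytosis should be based on other measurable aspects of disease other than ALC".

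**Eligibility.** Section 3.1.2 states that "Patients with CLL/SLL must demonstrate active disease meeting at least 1 of the IWCLL 2008 criteria for requiring treatment". Progressive lymphocytosis alone, or progressive marrow failure alone, is enough. The measurable-node requirement (the first item numbered 3.1.4) exempts CLL.

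**The concern.** The section that site staff and analysts will use to score response carries an ORR definition that conflicts with the objective, and the statistical section does not say which governs. ORR is the first secondary endpoint listed. It is also an outcome for the exploratory comparisons by del(17p)/del(11q), IGHV, TP53 and prior kinase inhibitor in 13.4.3.

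The PR rule raises a different problem. If a patient's disease sits in one compartment only, the number of criteria that patient can meet is limited before treatment starts. A real partial response may then be scored SD because of where the disease was. Subgroup ORRs would reflect disease distribution as well as drug effect. In a group of 17, one misclassified patient moves ORR by 1/17 = 5.9 percentage points, and by more within a subgroup.

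**Working it through.** The plan states no figure for this point, so the check is a comparison of texts followed by a count.

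**Step 1. The ORR sentence.** The six categories in the 11.2.1 sentence (CR, CRi, nPR, PR, PD, SD) cover every assessed patient, because SD is defined there as whatever is neither response nor progression. Taken literally, ORR is 100% of assessed patients. Illustration with the phase 2 sample size of 17 and an assumed 10 responders:

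- Section 1.2: 10/17 = 58.8%, Clopper-Pearson 95% CI 32.9% to 81.6%.
- Section 11.2.1 read literally: 17/17 = 100%, lower limit 0.025^(1/17) = 80.5%.

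**Step 2. What the PR rule allows, by baseline pattern.** The lymphocyte criterion is a fall from the pre-therapy value and needs no raised baseline, so it is open to everyone. The node criterion needs enlarged nodes, and the organ criterion needs organomegaly.

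| Baseline pattern | Most criteria attainable | PR under the two-of-three rule |
|---|---|---|
| No enlarged nodes, no organomegaly (blood-only or marrow failure only) | 1 (lymphocytes) | Impossible; CR, CRi and nPR remain |
| Nodes only, normal ALC | 2 (nodes, plus a 50% fall from a normal count) | Possible, by that route only |
| Organomegaly only | 2 (organ, plus lymphocyte fall) | Possible, if one enlarged organ satisfies a criterion that names both spleen and liver |
| Nodes and lymphocytosis, no organomegaly, ALC falls by half | 2 | Possible |
| Nodes and lymphocytosis, no organomegaly, ALC stays high | 1 (nodes) once ALC is set aside | Not stated |
| Nodes and organomegaly | 3 | Possible |

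The first row is an eligible CLL population under 3.1.2 and 3.1.4. Such a patient who improves short of CR, CRi or nPR, without progressing, falls to SD. In the fifth row, two careful readers could score the same patient PR or SD.

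**Step 3. Possible size.** Let s be the share of patients barred from PR. Assume that they have the same underlying response as the others, that CR is 20% (the null rate in 13.5), and that all other responses are PR. Then

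observed ORR = CR + (true ORR − CR) × (1 − s).

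The true ORR is set, for illustration only, to the two background figures in 13.5: 61% (entospletinib) and 77.3% (obinutuzumab with chlorambucil).

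- 61%, s = 5%: 0.20 + 0.41 × 0.95 = 58.95%
- 61%, s = 10%: 0.20 + 0.41 × 0.90 = 56.9%
- 61%, s = 20%: 0.20 + 0.41 × 0.80 = 52.8%
- 77.3%, s = 5%: 0.20 + 0.573 × 0.95 = 74.4%
- 77.3%, s = 10%: 0.20 + 0.573 × 0.90 = 71.6%
- 77.3%, s = 20%: 0.20 + 0.573 × 0.80 = 65.8%

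The loss is s × (true ORR − CR): 2.05 to 8.2 points in the first case and 2.9 to 11.5 in the second. The documents do not give s.

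**The case against.** The ORR sentence looks like a list of assessment categories that ran into the definition. An analyst who reads 1.2, or the SD definition a page later, would not count progression as response. That is fair, and a reported ORR of 100% is unlikely. It remains true that the operational section states a wrong rule and that section 13 does not override it.

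A reader might infer that node-only SLL can never be PR. The documents do not support that. The lymphocyte criterion is relative to the pre-therapy value, so a 50% fall from a normal count meets it. The route is realistic: sections 2.3.2.1 and 2.3.4 report extensive B-cell depletion with obinutuzumab. What stands is a validity weakness, since PR would then hinge on a count that was never abnormal.

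A reader might also infer that the two-of-three rule nullifies PR with lymphocytosis. That paragraph reads naturally as an exception to the general rule. Its defect is narrower: it does not say how many of the remaining criteria suffice.

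The two-compartment requirement may be deliberate. The section attributes its criteria to modified IWCLL guidelines, which are not part of the documents, so whether the wording departs from them cannot be judged here.

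Finally, section 13.1 describes the phase 2 efficacy endpoint with both ORR and CR in brackets, which might suggest that the go/no-go decision is exposed. Sections 1.1.2, 13.2.1, 13.4.1 and 13.5 all rest the primary endpoint and the 7-of-17 rule on CR. Neither the ORR nor the PR wording affects them.

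**Conclusion.** The concern holds in two parts, and its severity is minor to moderate.

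1. The ORR sentence in 11.2.1 contradicts section 1.2 and 11.2.1's own treatment of SD. This needs no assumption. It gives a wrong result if followed.
2. The PR rule is incomplete. PR is closed to eligible CLL without enlarged nodes or organs. It depends on a fall in a normal lymphocyte count for node-only disease with normal ALC. It is undefined for nodes with persistent lymphocytosis and no organomegaly.

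The effect is confined to the secondary ORR and the exploratory estimates built on it. Its size is unknown because the documents give no share of affected patients. The ranges under the working (about 2 to 8 points on a true ORR of 61%, about 3 to 11 on 77.3%) rest on an assumed 5% to 20% barred from PR, an assumed CR of 20%, and equal underlying response in that group. They cover only the barred group, not the ambiguous lymphocytosis cases.

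**What to change.** Before ORR is derived, amend 11.2.1 in one edit:

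- Change the ORR sentence to CR, CRi, nPR and PR (including PR with lymphocytosis), and state that SD and PD are non-responses, so that it matches 1.2.
- State that the PR criteria apply to compartments abnormal at baseline. Say how many must be met when only one is abnormal, when none is (marrow failure only), and when ALC is set aside for lymphocytosis.

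The cost is wording plus a re-derivation of response from lymphocyte counts, CT and examination data that the schedule already collects. No new procedure is needed.

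There is a downside. Some PRs will rest on one compartment, and a blood-only PR may be easy to reach with a B-cell-depleting antibody, especially as the accompanying blood-count result may already have been normal at baseline. Relaxing the rule could therefore raise ORR for the wrong reason. Flag these patients in the response listing and report ORR with and without them.
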